12.9.1 Reporting a Study Halt

If a halting rule is met, a description of the AE(s) or safety issue must be reported by the PI within 1 business day to the CSO and to the FMPOS EC according to their requirements. The PI will also notify the DSMB and ISM through the specified pathway.

12.9.2 Resumption of a Halted Study

The CSO, in collaboration with the PI, DSMB, and ISM, will determine if it is safe to resume the study. The conditions for resumption of the study will be defined in this notification. The PI will notify the EC of the decision on resumption of the study. Subjects who do not resume study

agent administration will continue to be followed for safety. They may also provide samples for immunology assays if the PI agrees that this is appropriate.

12.10 Early Termination of Study

The NIAID/OCRPRO as the study sponsor, FMPOS EC, or the FDA may terminate this study at any time. Reasons for terminating the study may include, but are not limited to, the following:

- The incidence or severity of an AE in this or other studies indicates a potential health hazard to subjects.
- Subject enrollment is unsatisfactory.
- Data recording is inaccurate or incomplete.
- Investigators do not adhere to the protocol or applicable regulatory guidelines in conducting the study.

12.11 Withdrawal Criteria for an Individual Participant

A subject will be withdrawn from the study for any of the following reasons:

- 1. Research terminated by Sponsor or Investigator applies to the situation where the entire study is terminated by the Sponsor or Investigator, or other regulatory authority for any reason.
- 2. Withdrawal of consent applies to a subject who withdraws consent to participate in the study for any reason after being enrolled (see Section 5.3). The investigator will attempt to determine the reason for the subject's decision and document it in the study chart.
- 3. *Non-compliance with protocol* applies to a subject who does not comply with protocol-specific visits or evaluations on a consistent basis, and to the extent that it is potentially harmful to the subject or to the integrity of the study data. This also applies to a subject who is lost to follow-up and is not reachable by telephone or other means of communication and cannot be located.
- 4. *At the PI's discretion* for any event that may pose a safety risk to the subject or jeopardize data collected for the study
- 5. *Other* is used when previous categories do not apply and a written explanation is required.

A withdrawn subject will not have any further study visits, safety evaluations, or research procedures for this protocol; however, any data collected from that subject prior to the withdrawal will be included in the safety and immunogenicity analysis if the subject completed at least 1 study vaccination.

If a subject withdraws or is withdrawn prior to completion of the study, the reason for this decision will be recorded in the source documents and CRFs. If the reason is not immediately clear, the investigator will make a reasonable effort to determine it.

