8.3 Early Termination Visit

If a subject withdraws or is withdrawn from the study after receipt of the first vaccination but before their final study visit, then they will be encouraged to return to the clinic for an Early Termination Visit, at which they will complete as many end-of-study visit procedures as possible.

9 Study Procedures/Evaluations

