12.4 Follow-up of Adverse Events and Serious Adverse Events

AEs that occur following receipt of a single vaccination are followed until the final outcome is known or until the end of the study follow-up period.

SAEs that have not resolved by the end of the follow-up period will be followed until final outcome is known. If it is not possible to obtain a final outcome for an SAE (e.g., the subject is

lost to follow-up), the last known status and the reason a final outcome could not be obtained will be recorded by the investigator on the AE CRF (if the CRF is still open) and by REDCap or on the Safety Expedited Report Form (SERF).

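### Section 12.11 bars all further visits and safety evaluations after withdrawal, while Section 8.3 invites the same vaccinated subjects back; read literally, 12.11 also stops safety evaluation of reachable, consenting vaccinees withdrawn under reasons 3 to 5

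*Combined protocol and SAP*

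**What the plan says.** Section 12.11 lists five reasons for withdrawal: (1) termination of the research, (2) withdrawal of consent, (3) non-compliance, which also takes in loss to follow-up, (4) the PI's discretion "for any event that may pose a safety risk to the subject or jeopardize data collected for the study", and (5) other. One rule then covers all five: "A withdrawn subject will not have any further study visits, safety evaluations, or research procedures for this protocol". For subjects with at least one vaccination, the section adds that "any data collected from that subject prior to the withdrawal will be included in the safety and immunogenicity analysis".

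Section 8.3 begins "If a subject withdraws or is withdrawn from the study after receipt of the first vaccination but before their final study visit". Such a subject is encouraged to come back for an Early Termination Visit, "at which they will complete as many end-of-study visit procedures as possible".

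Section 5.3 counts a participant as withdrawn once any 12.11 criterion is met before the final visit is completed. Section 12.4 follows adverse events after vaccination to outcome or to the end of study follow-up, and adds: "SAEs that have not resolved by the end of the follow-up period will be followed until final outcome is known". Section 12.5.5 plans collection of medically attended adverse events (MAAEs) in all treatment groups through 12 months after the last vaccination, because of a theoretical autoimmune risk from the adjuvant.

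**The concern.** At the moment a vaccinated subject leaves, site staff have two instructions that cannot both be followed as written: no further visits, and an invitation to a visit.

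The bar is also wider than respect for consent requires. Only reason 2 is a withdrawal of consent. Under reasons 3 to 5 the subject may be reachable and willing, and under reason 4 the cause may itself be a safety concern. In a first-in-human trial that does not replace vaccinated withdrawals (12.11.1), applying 12.11 literally would end active safety observation of someone whose later course is of particular interest. At stake are active ascertainment of later adverse events and MAAEs and, to the extent that 12.11 is taken to override 12.4, the outcomes of events still open at exit.

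**Working it through.** The plan states no figure on this point, so the check is a comparison of the sections, followed by a count from Appendix A.

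**Same people.** Section 8.3 covers subjects who leave, or are removed, between the first vaccination and the final visit. Under 5.3, withdrawn status attaches when a 12.11 criterion is met. A vaccinated subject withdrawn before the final visit therefore falls under both rules. Subjects withdrawn between Day -7 and dose 1 fall under 12.11 only, so there is no contradiction for them.

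**Opposite actions.** Section 12.11 rules out further visits, safety evaluations and research procedures. Section 8.3 asks for a return visit with end-of-study procedures. Neither section excepts or cites the other.

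**Who may be reachable and consenting, by reason.**
- Reason 2: consent is withdrawn, so ending follow-up is proper; the exit visit remains a matter for the subject.
- Reason 3: a non-compliant subject may be reachable. One lost to follow-up is not, and is outside the point.
- Reasons 4 and 5: neither requires loss of contact or of consent.

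**Other sections.** Section 12.4 has no stop at withdrawal, so it conflicts with the ban on safety evaluations. Section 12.5.5 does not mention withdrawn subjects, so the tension there is by implication only.

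**Contacts forgone per subject.** After dose 3 (Day 57), Appendix A schedules contacts at +1, 3, 7, 14, 28, 56, 84, 168, 224, 280 and 336 days, which is 11 contacts. The last falls on Day 57 + 336 = 393.

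| Withdrawal after dose 3 | Contacts forgone | Days unobserved |
|---|---|---|
| Day of dose | 11 | 336 |
| At the +7 visit | 11 - 3 = 8 | 336 - 7 = 329 |
| At the +14 visit | 11 - 4 = 7 | 336 - 14 = 322 |

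If 8.3 prevails, one exit visit is recovered and the period after it is still unobserved. No count is offered for withdrawal after dose 1 or 2, because Appendix A fixes the later visits relative to dose 3.

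**Scale, by assumption.** Scheduled visits total 80 × 23 = 1,840. If 1 to 4 subjects withdrew on the day of dose 3, the contacts forgone would be 1 × 11 = 11 to 4 × 11 = 44, or 0.6% to 2.4% of 1,840. The range 1 to 4 is an assumption, so this illustrates the scale and does not bound it.

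**The case against.** The best defence is that 8.3 is the specific provision, the visit is voluntary, and 12.11 describes what follows once that exit step is done. This may well be what was intended. The text does not say so, however, and 5.3 attaches withdrawn status before any return visit. The defence shows that the repair is small; it does not make the two sections consistent. It also leaves the period after the exit visit untouched.

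The protocol also separates stopping vaccine from leaving the study. Subjects are kept in follow-up, or encouraged to stay, after a contraindication (7.4), deferral (7.5), prohibited medication (7.7), a pause (12.8.3), a halt (12.9.2) or unblinding (14.5.3). An investigator with a safety concern can pause dosing without withdrawing anyone (12.8.1). Related SAEs reported after the final visit still go to the sponsor's safety office (12.5.2). All of this stands, and it is why few subjects should be affected. The retention routes cover people who remain in the study, though, and the late SAE route depends on a report being made.

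Three stronger readings are tempting and are not supported:
- A reader might infer that data gathered after withdrawal are excluded from analysis. Section 12.11 says that earlier data are included; it is silent on later data.
- A reader might infer that open adverse events are simply abandoned. Section 12.4 follows both non-serious and serious events and can be read to continue after withdrawal. The documents show a conflict between sections, not a settled loss.
- A reader might extend the point to termination of the whole trial, since reason 1 "applies to the situation where the entire study is terminated by the Sponsor or Investigator, or other regulatory authority for any reason" and the first ground in 12.10 is that "The incidence or severity of an AE in this or other studies indicates a potential health hazard to subjects". The wording of the bar does reach that case. But 12.10 sets out no follow-up arrangements after termination, so the documents give no basis for a remedy there. Such a remedy could involve up to 80 subjects, and nothing says who would run the contacts.

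**Conclusion.** The contradiction between 8.3 and 12.11 is certain from the text for vaccinated subjects. The second part, loss of safety evaluation for reachable, consenting vaccinees withdrawn under reasons 3 to 5, holds on a literal reading of 12.11. It conflicts with 12.4 and sits badly with 12.5.5.

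The size is modest. After dose 3, up to 11 contacts per subject could be forgone. How many subjects would be affected is unknown. The earlier Alhydrogel trial reports no removals for a related adverse event (3.1.1), which suggests few, although the adjuvant differed. Because no withdrawal rate is given, a trial-wide cap on lost contacts cannot be derived. A reader might infer bias or a material loss of power; neither is claimed, since data collected before withdrawal are retained and the likely number is small. The point should be fixed because it concerns safety follow-up in a first-in-human trial and the repair is cheap.

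**What to change.** Amend 12.11 so that after withdrawal no further study vaccine is given and no research procedures are done, with two exceptions:

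- (a) The Section 8.3 Early Termination Visit, for any vaccinated subject who agrees to it.
- (b) For vaccinated subjects withdrawn under reasons 3 to 5 who are reachable and still consent, AE and SAE follow-up under 12.4 and MAAE contact under 12.5.5 through 12 months after the last dose received. Phone contact is acceptable.

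State that data from (a) and (b) enter the safety analysis, and cross-reference 8.3 and 12.11. Subjects who cannot be located remain lost to follow-up under 5.3.

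The cost is a short amendment with ethics committee approval under 16.3, where expedited review may be requested for changes that do not affect risk. Consent wording may need to match; the consent pages were not available to check. Each affected subject adds an exit visit and a few contacts. Section 8.2 already allows phone calls for the last three scheduled visits.

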12.11.1 Replacement of Withdrawn Participants

Subjects who withdraw or are withdrawn from the study after receiving at least 1 study vaccination will not be replaced. Subjects withdrawn before the first vaccination may be replaced.

12.12 Safety Oversight

12.12.1 Safety Review and Communications Plan

A Safety Review and Communications Plan (SRCP) has been developed for the protocol. The SRCP is an internal communications document between the PI and the CSO, which delineates the safety oversight responsibilities of the PI, the CSO, and other stakeholders. The SRCP also includes the overall plan for conducting periodic safety surveillance assessments.

12.12.2 Sponsor Medical Monitor

A medical monitor, representing the IND sponsor (OCRPRO), has been appointed for oversight of safety in this clinical study. The sponsor medical monitor will be responsible for performing safety assessments as outlined in the SRCP.

12.12.3 Independent Safety Monitor (ISM)

An ISM in Mali will review the study prior to initiation and will be available to advise the investigators on study-related medical issues and to act as a representative for the welfare of the subjects. The ISM will conduct independent safety monitoring and recommend appropriate action regarding AEs and other safety issues. The ISM is an expert in the field of oversight of clinical trials conducted in Mali and internal medicine, specifically in the population under study in Mali. The ISM does not have direct involvement in the conduct of the study and does not have other interests with any collaborating pharmaceutical firms or their competitors. The ISM will remain blinded throughout the study.

Prior to each ISM review (including DSMB meeting safety reports and at least twice yearly reviews), the PI will provide a safety summary report (similar to the DSMB safety reports). After each ISM review, a recommendation as to whether the study is to be modified or terminated will be provided in a summary report to the study PI. If the study is to continue as is, no report will need to be submitted by the ISM except for communication to the PI that the review has been completed (via in-person communication, phone, or email). All SAEs, all UPs, and all IND Safety Reports will be reported by the PI to the ISM at the same time they are submitted to the EC or IND sponsor. The ISM will be notified immediately if any pausing or halting rule is met and the ISM will provide recommendation for continuation, modification, or termination of the study. The PI will submit the written ISM summary report with the recommendations to the EC on a biannual basis or more frequently if a safety concern is raised.

12.12.4 Data and Safety Monitoring Board (DSMB)

The NIAID intramural DSMB includes independent experts that do not have direct involvement in the conduct of the study and have no significant conflicts of interests as defined by NIAID policy. The DSMB will review the study prior to initiation and at the end of the study, and may convene additional reviews as necessary. The board will review the study data to evaluate the safety, efficacy, study progress, and conduct of the study. All SAEs, all UPs, and all IND Safety Reports will be reported by the PI to the DSMB at the same time they are submitted to the EC or IND sponsor. The PI will notify the board at the time pausing or halting criteria are met and obtain a recommendation concerning continuation, modification, or termination of the study. The PI will submit the written DSMB summary reports with recommendations to the FMPOS EC.

13 Site Monitoring Plan

According to the International Conference on Harmonisation (ICH) E6(R2) Good Clinical Practice (GCP) guidelines, section 5.18, and FDA 21 CFR 312.50, clinical protocols are required to be adequately monitored by the study sponsor. This study monitoring will be conducted according to the "NIAID Intramural Clinical Monitoring Guidelines." Monitors under contract to the NIAID/OCRPRO will visit the clinical research site (or conduct virtual site visits) to monitor aspects of the study in accordance with the appropriate regulations and the approved protocol. The objectives of a monitoring visit will be: 1) to verify the existence of signed informed consent documents and documentation of the consent process for each monitored subject; 2) to verify the prompt and accurate recording of all monitored data points and prompt reporting of all SAEs; 3) to compare abstracted information with individual subjects' records and source documents (subjects' charts, laboratory analyses and test results, physicians' progress notes, nurses' notes, and any other relevant original subject information); and 4) to help ensure investigators are in compliance with the protocol. The monitors also will inspect the clinical site regulatory files to ensure that regulatory requirements (Office for Human Research Protections [OHRP], FDA) and applicable guidelines (ICH GCP) are being followed. During the monitoring visits, the investigator (and/or designee) and other study personnel will be available to discuss the study progress and monitoring visit.

The investigator (and/or designee) will make study documents (e.g., consent forms, DataFax data abstracts) and pertinent hospital or clinical records readily available for inspection by the FMPOS EC, FDA, the site monitors, representatives of the PfTBV EDCTP Consortium and the NIAID staff for confirmation of the study data.

A specific protocol monitoring plan will be discussed with the PI and study staff prior to enrollment. The plan will outline the frequency of monitoring visits based on such factors as study enrollment, data collection status, and regulatory obligations.

14 Statistical Considerations and Sample Size

14.1 Sample Size

Safety:

The arms are sufficiently sized for safety. For each dose level (n=20) in Arms 1a combined with 2a, and 1b combined with 2b, 1c combined with 2c, and 1d combined with 2d, vaccination of 20 subjects gives a power of at least **0.80** for detecting 1 or more serious or severe AEs that occur with a probability of **0.077** or more per subject (or **0.90** for an event with a probability of **0.109**).

If we combine all treated groups (arms 1a/2a, 1b/2b, 1c/2c), with a total of 60 subjects, we have **80% power** to detect 1 or more serious or severe AEs that occur with a probability of **0.026** or more per subject (or **0.90** for an event with a probability of .037).

The aforementioned calculations do not assume any historical data; they are statistical consequences of the binomial distribution.

We will compare all AE event proportions between the control arm and treated arm by Fisher's exact test.

Immunogenicity:

We plan to do a test for an overall signal with a global analysis. That is, we will combine arms 1a/2a, 1b/2b, and 1c/2c into an "any vaccination" group of n=60 and combine arms 1d and 2d into a "control" group of n=20. Using historical data from the AS01 trial, we are well powered to detect a log difference (>99.9% power) and ½ log difference (99.7% power).

Following this global test, testing specific arms is of interest. To adjust for multiplicity, we use Bonferroni corrected alpha of 0.05/3. To investigate the specific arms we conduct three tests: arms 1a/2a vs controls, arms 1b/2b vs controls, and arms 1c/2c vs controls. The controls use arms 1d and 2d. This makes each analysis n=20 vs n=20. As such, we are well powered to detect a log difference (>99.9% power) and ½ log difference (89.2% power).

These calculations were made assuming normal distributions with mean and standard deviations from the AS01 trial. 1000 simulations were run to see how often a significant result came from a Wilcoxon-Mann-Whitney test (WMW).

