NCT03970993	VAC 072-An Efficacy Study of R21/MM in Different Dose Schedules	Malaria	Biological: R21 Matrix-M vaccination Biological: R21 Matrix-M vaccination and CHMI	Phase 1 Phase 2	18 Years to 45 Years (Adult)
NCT02370589	Study to Evaluate the Immunogenicity and Safety of an Ebola Virus (EBOV) Glycoprotein (GP) Vaccine in Healthy Subjects	Ebola	Biological: Base Dose EBOV GP Vaccine Biological: 2-8x Base Dose EBOV GP Vaccine Biological: Matrix-M Adjuvant	Phase 1	18 Years to 50 Years (Adult)
NCT02515175	Evaluating New Formulation of Therapeutic HSV-2 Vaccine	Genital Herpes	• Biological: Matrix-M2 • Biological: GEN-003	Phase 2	18 Years to 50 Years (Adult)
NCT04120194	Phase 3 Pivotal Trial of NanoFlu™ in Older Adults	Influenza	Biological: NanoFlu Biological: Fluzone Quadrivalent	Phase 3	65 Years and older (Older Adult)
NCT04645147	Safety and Immunogenicity of an Epstein- Barr Virus (EBV) gp350-Ferritin Nanoparticle Vaccine in Healthy Adults With or Without EBV Infection	EBV	Biological: EBV gp350- Ferritin Vaccine Other: Matrix-M1	Phase 1	18 Years to 29 Years (Adult)
NCT03146403	Maintenance Dose Study of GEN-003 in Subjects With Genital Herpes Infection	Genital Herpes	• Biological: GEN-003 • Biological: Matrix-M	Phase 2	Child, Adult, Older Adult

NCT Number	Title	Conditions	Interventions	Characteristics	Population
NCT02905019	A Safety and Efficacy Study of R21 +/- ChAd63/MVA ME-TRAP	Malaria	Biological: R21 with Matrix- M1 Biological: ChAd63 ME-TRAP Biological: MVA ME-TRAP	Phase 1 Phase 2	18 Years to 45 Years (Adult)

4 Study Objectives

Primary Objective:

• To assess in African adults the safety and the reactogenicity of administration of Pfs230D1-EPA/Matrix-M (first-in-human) as compared to the rabies vaccine control

Secondary Objectives:

- To assess level of and duration of humoral immune responses as measured by ELISA titer response to Pfs230D1M after third immunization
- To assess the functional antibody response by SMFA to Pfs230D1M

Exploratory Objectives:

- To explore cellular and humoral responses to Pfs230D1M
- To analyze innate and adaptive states before and at early timepoints after vaccination by using RNA sequencing
- Estimation of interaction between host factors including but not limited to hemoglobinopathies, immune genes signatures, co-infections, and environmental, demographic, and socioeconomic characteristics and primary and secondary endpoints

5 Study Design

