14.2 Primary Objective

To assess safety and reactogenicity of administration of Pfs230D1-EPA/Matrix-M (all Arms):

- The frequency of systemic and local AEs will be summarized.
- A line listing of each clinical and laboratory AE classified as local, solicited, or other will be displayed in tables stratified by vaccine allocation.

- AEs will be summarized by severity and relationship to vaccine.
- The proportion of subjects with at least 1 AE will be compared by study group, and tests will be performed to assess whether these groups differ with respect to these proportions. To evaluate the difference in AEs between the initial vaccination and the subsequent vaccinations, a Wilcoxon signed-rank test (WSRT) will be performed, where the response for each subject is the difference between the numbers of AEs in the 7 days following each vaccination. To compare number and severity of AEs between control and vaccine arms, the Wilcoxon-Mann-Whitney test (WMW, also known as Wilcoxon rank sum test and Mann-Whitney U test) as well as linear regression may be used.
- SAEs occurring within the study period will be listed by relationship to vaccine.

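### The safety power in 14.1 is the chance of seeing at least one event in a single arm; it does not size the planned comparison with rabies vaccine, for which a more powerful exact test than Fisher's is available

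*Combined protocol and SAP*

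**What the plan says.** The primary objective (section 4) is comparative: "safety and the reactogenicity of administration of Pfs230D1-EPA/Matrix-M (first-in-human) as compared to the rabies vaccine control".

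Section 14.1, Safety, states that "The arms are sufficiently sized for safety". Its support is that "vaccination of 20 subjects gives a power of at least 0.80 for detecting 1 or more serious or severe AEs" at a per-subject probability of 0.077, or 0.90 "for an event with a probability of 0.109". For the 60 pooled vaccinees it gives 80% at 0.026 and 0.90 at 0.037. The basis is disclosed: "The aforementioned calculations do not assume any historical data; they are statistical consequences of the binomial distribution".

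The next sentence sets out a between-arm analysis: "We will compare all AE event proportions between the control arm and treated arm by Fisher's exact test". Section 14.2 adds a test for unequal proportions without naming it (the quote is cut short): "The proportion of subjects with at least 1 AE will be compared by study group, and tests will be performed to assess whether these groups". Section 14.4.1 describes the primary safety analysis as a comparison of AE rates between vaccinated and control individuals. For safety, no alpha, sidedness, control rate or detectable difference is stated.

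**The concern.** The only quantitative support for the safety sample size uses no control arm and no test, while the plan commits to comparing AE proportions with the rabies arm. The immunogenicity part of 14.1 does the matching work: its power is simulated with the planned Wilcoxon-Mann-Whitney test on the planned contrasts. The safety comparison has no equivalent.

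At the event rates quoted, a non-significant between-arm test is close to certain whatever the truth. Placed next to a printed 80%, such a result carries a risk of misreading in a first-in-human trial. For common reactions, where the comparison can be informative, the choice of Fisher's test gives up power that another exact test keeps at the same 5% level.

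**Working it through.** **Inputs.** Arm sizes from 5.2 and 14.1: 20 per dose level, 60 pooled, 20 controls. Event probabilities from 14.1: 0.077 and 0.109 (n=20), 0.026 and 0.037 (n=60). Assumed, because the plan does not state them for safety: two-sided alpha 0.05 (the level 14.3.1 gives for an ELISA test), no multiplicity correction, and a control rate of 0%, which is the most favourable case for showing an excess.

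**Step 1: reproduce the printed figures.** P(at least one event) = 1 − (1 − p)^n.
- n=20, p=0.077: 0.799 (printed 0.80)
- n=20, p=0.109: 0.901 (printed 0.90)
- n=60, p=0.026: 0.794 (printed 80%)
- n=60, p=0.037: 0.896 (printed 0.90)

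All four agree to rounding. None involves the comparator.

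**Step 2: what Fisher's test needs when the control arm has 0/20 events.**
- 20 vs 20: p = 2 × C(20,x)/C(40,x). For x=4 this is 2 × 4845/91390 = 0.106; for x=5 it is 2 × 15504/658008 = 0.047. At least 5/20 is needed.
- 60 vs 20: 11/60 gives p = 0.057 and 12/60 gives p = 0.031. At least 12/60 is needed.

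**Step 3: Fisher power at the printed rates, 0% control.** Power is then P(X ≥ 5 | 20, p) or P(X ≥ 12 | 60, p).

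| Comparison | Event rate | Printed one-arm figure | Fisher power |
|---|---|---|---|
| 20 vs 20 | 0.077 | 0.80 | 1.6% |
| 20 vs 20 | 0.109 | 0.90 | 5.9% |
| 60 vs 20 | 0.026 | 0.80 | about 0% |
| 60 vs 20 | 0.037 | 0.90 | about 0% |

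**Step 4: sensitivity, by enumerating all 2×2 tables.** With control rates of 1% to 5%, 20 vs 20 gives 0.6–1.3% at 0.077 and 2.3–4.9% at 0.109. For 60 vs 20 the power is at most 4.5%, nearly all of it rejection in the wrong direction (control higher). One-sided 0.05 stays within 0–5.9%. Two-sided 0.05/3 gives at most 0.4% in 20 vs 20.

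**Step 5: the choice of test.** The maximum true size of Fisher's test over all common rates is 2.5% (20 vs 20) and 3.6% (60 vs 20). Boschloo's test, ordered by the two-sided Fisher p-value and maximised over a 999-point grid of the common rate, has maximum size 4.6% and 4.9%, and it rejects wherever Fisher's does.

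For common reactions, 3.2.1 gives Grade 1 injection-site pain per dose in the AS01 trial: 95/168 = 57% in the full-dose arm and 39/360 = 11% in controls. These are used here as illustrative per-subject rates.

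| Rates | Comparison | Fisher | Boschloo |
|---|---|---|---|
| 50% vs 11% | 20 vs 20 | 71% | 79% |
| 57% vs 11% | 20 vs 20 | 85% | 90% |
| 0.077 or 0.109 vs 0% | 20 vs 20 | 1.6% or 5.9% | the same |
| 20% vs 0% | 60 vs 20 | 55% | 79% |

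The last row depends on how the two-sided test is defined. Boschloo's test ordered by the two-sided Fisher p-value rejects at 10/60 vs 0/20. One common software routine uses another two-sided definition, gives p = 0.057 for that table and does not reject, which leaves about 68%.

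**Step 6: rates detectable with 80% power (two-sided 0.05, uncorrected).**

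| Control rate | 20 vs 20 Fisher | 20 vs 20 Boschloo | 60 vs 20 Fisher | 60 vs 20 Boschloo |
|---|---|---|---|---|
| 0% | 31.5% | 31.5% | 24% | 20.5% |
| 5% | 44.5% | 40% | 34.5% | 32.5% |

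**The case against.** The strongest reply is that 14.1 contains no error. It says openly that the power is for detecting one or more events, attributes it to the binomial distribution, and applies the same figure to the control arm itself, which no comparative power could do. This is a usual Phase 1 statement. It stands: a reader might infer that the 0.80 and 0.90 are miscalculated, or that 14.1 claims 80–90% power for the comparison with rabies vaccine, and the text supports neither reading.

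A reader might also infer that Fisher's test is the whole primary analysis. It is not. Section 14.2 is largely descriptive, names no test for proportions, allows Wilcoxon-Mann-Whitney and linear regression for number and severity of AEs, and lists SAEs by relationship. Decisions on serious events rest on the halting rules in 12.9, where a single related SAE is enough, and on DSMB review (12.12.4). For those, the chance of seeing at least one event is a relevant quantity. No section says that a non-significant test will be taken as similar safety.

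Power is also not poor throughout. For large reactogenicity differences such as 57% vs 11%, Fisher's test already has 85% in 20 vs 20 and 98% in 60 vs 20.

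These replies narrow the point but do not remove it. Section 14.1 still sends all AE proportions to a between-arm test, and nothing printed shows what that test can detect.

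**Conclusion.** The point holds in a limited form. The printed figures are correct for single-arm detection, and the statement on sufficient size is justified only in that sense. For the comparison of AE proportions with rabies vaccine planned in 14.1, 14.2 and 14.4.1, Fisher's test at the same event rates has 1.6% and 5.9% power (20 vs 20) and about 0% (60 vs 20). This assumes two-sided 0.05 and 0% control. The conclusion is insensitive to control rates up to 5%, to one-sided testing and to a Bonferroni level.

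The gain from changing the test is real but confined to common events: 8 points at 50% vs 11% (71% to 79%) and 5 points at 57% vs 11% (85% to 90%) in 20 vs 20. There is no gain at the rare-event rates in 20 vs 20, or anywhere in 20 vs 20 against 0% control; 60 vs 20 stays at about 0% at the printed rates. The gain for common events rests on treating per-dose rates as per-subject rates.

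**What to change.** 1. In 14.1, and by reference in 14.2, replace Fisher's exact test for AE proportions with Boschloo's unconditional exact test. State that the two-sided Fisher p-value is the ordering statistic, because other two-sided definitions give different results for 60 vs 20. Its power is never below Fisher's and the 5% level is kept.
2. Label the 0.80 and 0.90 as the probability of observing at least one event in the group, and limit the sizing statement to that purpose.
3. State alpha and sidedness for the safety comparison, whether the three dose-level comparisons are corrected for multiplicity, and the differences detectable with 80% power. For Boschloo at two-sided 0.05, uncorrected: 20 vs 20, about 31.5% vs 0%, 40% vs 5% and 50.5% vs 11%; 60 vs 20, about 20.5% vs 0% and 32.5% vs 5%.
4. Report exact 95% confidence intervals for each arm's rate and for the risk differences, and say that a non-significant result on serious or severe AEs is not evidence of similar safety.

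The cost is wording in 14.1 and 14.2, a less familiar test, and a check that the software uses the stated ordering. No participants, visits or data are added. The stated safety sensitivity will look less favourable.
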